	
Cohort 1. Subjects who opt for an optic exchange procedure will be entered into Cohort 2.
 
All fellow eyes will receive a commercially approved IOL and standard of care (SOC) follow-up for 12 Months.
 
For purposes of accountability and analysis, there will be the following Cohorts:
 
 • All HMIOL Eyes Cohort (All eyes receiving study device) • HMIOL Cohort 1 (HMIOL eyes without optic exchange) • HMIOL Cohort 2 (HMIOL eyes with optic exchange) • Fellow Eyes Cohort 
Post-Operative Visits
 
All HMIOL Eyes Cohort
 
 • 1 Day, 1 Week, 1 Month, 3 Month following primary cataract extraction 
HMIOL Cohort 1 (HMIOL subjects without optic exchange procedure)
 
 • 6 Month, and 12 Month Visits following primary cataract extraction 
HMIOL Cohort 2 (HMIOL subjects undergoing optic exchange)
 
 • Optic exchange decision and assignment to Cohort 2 at 3 Month Visit as deemed necessary by Investigator and Subject • 1 Day, 1 Week, 1 Month, 3 Month, 6 Month, and 12 Month Visits following optic exchange 

Study Endpoints
	
The safety and effectiveness of HMIOL for the treatment of aphakia in subjects following cataract extraction will be characterized along with the safety and effectiveness of the HMIOL optic exchange procedure in the subgroup of study subjects with optic exchange.
 
Safety Endpoints:
 
All HMIOL Eyes Cohort:
 
 • 

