3.0 STUDY DESIGN

3.1 DESCRIPTION OF THE STUDY

This is a prospective, multi-center, feasibility study being conducted at up to 7 investigative sites. All sites will have Institutional Review Board (IRB) or Ethics Committee (EC) review and approval prior to recruiting potential subjects. Up to 200 eligible subjects with bilateral cataracts will undergo cataract extraction in each eye during participation. Within approximately one to four weeks post-implantation of the HMIOL, the fellow eye (FE) will be implanted with a commercially available IOL.

At the 3 Month Visit (post-primary cataract extraction), subjects with satisfactory outcomes, or those opting not to pursue an optic exchange, will be entered into Cohort 1.

Subjects who opt for an HMIOL optic exchange in their primary eye will be entered into Cohort 2.

[figure not shown]

FIGURE 2 - COHORT DESIGNATION

All subjects enrolled in this study will be evaluated for 12 months following either primary cataract extraction or optic exchange, whichever is later (see Appendix A – Schedule of Assessments).

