At the 3 month visit, an overall assessment of a subject's visual function will be performed by the physician. If the physician's assessment results in an opportunity for improved visual function through optic exchange in the test eye, the subject will be offered that opportunity. The Investigator and the Subject will decide if an optic exchange is appropriate.

The decision will be documented and the prospective Cohort indicated.

- If the subject has an acceptable outcome or it is otherwise decided an optic exchange will not take place, the subject will be entered into Cohort 1 and be followed at the 6 and 12 Month Visits prior to study completion. If the subject desires an exchange, however it is decided they cannot have one based on exclusion criteria (Section 3.2.4), the subject will remain in Cohort 1 and can utilize spectacles to correct RRE for the remainder of study participation. The investigator and subject can decide on further treatment per the Investigator's standard of care, following study participation.
- If it is decided an HMIOL optic exchange is desired, the appropriate pre-operative measurements will be obtained, 3 Month Visit assessments completed per Appendix A – Table 1, and HMIOL calculations and optic ordered. Finally, the subject will be scheduled for the procedure and entered into Cohort 2 (finalized after successful completion of optic exchange). If for any reason the optic exchange procedure does not take place, the subject will default back to Cohort 1.

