3.3.5 COHORT 1: 6 AND 12 MONTH VISITS

All subjects entered into Cohort 1 will be seen for 6 and 12 Month Visits (post-primary cataract extraction) for bilateral assessments and exited from the study (See Appendix A – Table 1).

NOTE: All concomitant medication, AE, ADE, DD, and SAE collection must be continued throughout the course of the study.

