3.3.6 COHORT 2: OPTIC EXCHANGE VISIT (3 MONTH VISIT +1-21 DAYS)

Record any changes in concomitant medications and prepare the subject for optic exchange surgery in the study eye (see Surgical Procedure Guide).

CLARVISTA MEDICAL

PROTOCOL CP-00001 Rev.05

The Investigator will carry out the optic power determination, surgical procedure, and HMIOL optic exchange as specified in the Surgical Guide and the following details will be captured in both Source Documents and eCRFs:

- Date of surgery
- Operative eye
- Incision location and size
- Ophthalmic Viscoelastic Device (OVD) used
- All medication used pre-, intra-, and post-operatively (ophthalmic and systemic)
- Surgical times
- Model, serial number, and diopter of HMIOL Optic
- HMIOL Optic injection device

Once the subject is confirmed stable post-surgery, provide IRB / EC approved post-operative instructions and discharge.

Following successful completion of HMIOL optic exchange, the subject is entered into Cohort 2. Record any AEs, ADEs, UADEs, or DDs (see Sections 6.1.1, 6.1.2, 6.1.3, or 6.1.4 respectively) observed pre-, intra-, or post-operatively.

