Several cohorts of subjects are specified to help characterize the clinical significance of the study outcomes in eyes with and without optic exchange. These cohorts are defined as follows:

All HMIOL Eyes Cohort: Defined as all study eyes implanted with the study device. Analysis of follow-up visits for this cohort definition is restricted to 1 Day, 1 Week, 1 Month, and 3 Months following primary cataract extraction (PCE).

Cohort 1: Defined as the subset of study eyes implanted with the study device without a subsequent optic exchange procedure. Analysis of follow-up visits for this cohort definition is restricted to 1 Day, 1 Week and 1, 3, 6 and 12 Months following primary cataract extraction.

Cohort 2: Defined as the subset of study eyes implanted with the study device with a subsequent optic exchange procedure. Analysis of follow-up visits for this cohort will cover two time periods:

- Pre-Optic Exchange, comprising 1 Day, 1 Week, 1 Month, and 3 Months following primary cataract extraction, prior to the optic exchange visit.
- Post-Optic Exchange, comprising 1 Day, 1 Week, 1 Month, 3 Months, 6 Months, and 12 Months following optic exchange. The baseline for the post-optic exchange visits is the 3 Month pre-optic exchange visit.

Fellow Eyes Cohort: Defined as the contralateral eyes not implanted with the study device. Analysis of follow-up visits for this cohort definition is restricted to 1 Day, 1 Week, 1 Month, 3 Months, 6 Months, and 12 Months following primary cataract extraction.

Separate analyses are planned for each cohort.

Protocol CP-00001

ClarVista Medical, Inc.

5. Statistical Analyses

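### The protocol makes Cohort 2 conditional on a successful optic exchange and the SAP does not, so a started-but-not-completed exchange changes cohort with the text applied

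*Protocol*

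**What the plan says.** **Protocol assignment.** At the 3 Month Visit (3.3.4) a prospective cohort is documented. A subject who wants an exchange is scheduled and "entered into Cohort 2 (finalized after successful completion of optic exchange". Section 3.3.6 confirms the second step: "Following successful completion of HMIOL optic exchange, the subject is entered into Cohort 2". Appendix A Table 3, the Cohort 2 schedule, is headed for completed exchanges. The only fallback is in 3.3.4: "If for any reason the optic exchange procedure does not take place, the subject will default back to Cohort 1". The Study Design part of the synopsis ("Subjects who opt for an optic exchange procedure will be entered into Cohort 2") and Section 3.1 ("Subjects who opt for an HMIOL optic exchange in their primary eye will be entered into Cohort 2") speak of election only.

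**SAP assignment.** SAP Section 4 has Cohort 2 "Defined as the subset of study eyes implanted with the study device with a subsequent optic exchange procedure". Cohort 1 is its complement, eyes without such a procedure. Neither definition mentions completion. SAP Section 2 says its analyses supersede those of the protocol.

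**What follows from the cohort.**
- Visits: Protocol 3.3.5 says "All subjects entered into Cohort 1 will be seen for 6 and 12 Month Visits (post-primary cataract extraction". Section 3.3.7 gives the series from 1 day to 12 months after exchange to Cohort 2 only.
- AE reporting: under Section 6.0 the period ends at the 12 Month Visit, counted from surgery for Cohort 1 and from exchange for Cohort 2.
- Secondary surgical interventions (SSI): the exclusion for optic exchanges appears for Cohort 2 only (Protocol 7.1, SAP 5.4).
- Endothelial cell count (ECC): the SAP 5.4 test is defined for eyes with an optic exchange.

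**The concern.** An exchange can be started and then abandoned with the HMIOL still in the eye. It was not successfully completed, so it misses the protocol's condition for Cohort 2. It is also not clearly an exchange that did not take place, so the fallback to Cohort 1 does not plainly apply. The SAP's wording can be read to include it in Cohort 2, but does not say so.

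Feasibility of the exchange is a stated objective (Protocol 2.0, SAP Section 1). If the protocol rule governs, Cohort 2 contains successes only. Its safety rates and the ECC test then describe exchanges that went well, and events from failed attempts move to Cohort 1, the no-exchange group, or sit in no cohort column. The choice also decides which scheduled visits the eye receives. If it is made after outcomes are known, it is open to bias.

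**Working it through.** The plan gives no exchange failure rate, so there is no figure of its own to reproduce on this point. The check compares the rules and then illustrates their effect.

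**1. The same eye under each text** (exchange started, not completed, HMIOL retained)
- Protocol 3.3.4 and 3.3.6: not Cohort 2. Cohort 1 only if an incomplete exchange is read as one that did not take place.
- SAP Section 4: Cohort 2 if a started procedure counts as a procedure; otherwise Cohort 1.
- Protocol 4.5: gives a path (one visit, then discontinuation) only if the HMIOL System is explanted. It names no cohort.

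**2. Effect on the ISO comparison**

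Inputs: 105 subjects and 44 exchanges are the minimums in Protocol 4.7.1, not planned sizes. All 105 are assumed implanted. The failures and events are assumed. The rule in SAP 5.4 is that an event is met when the exact one-sided 95% lower bound is below the threshold in SAP Table 1.

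For one event in n eyes the bound solves 1 − (1 − L)^n = 0.05, so L = 1 − 0.95^(1/n). Take one failed exchange in addition to 44 completed, with one event whose threshold is 0.1% (endophthalmitis, lens dislocation or pupillary block):
- In Cohort 2: n = 44 + 1 = 45; L = 1 − 0.95^(1/45) = 0.114%. Not met.
- In Cohort 1: n = 105 − 44 = 61, failed eye included; L = 1 − 0.95^(1/61) = 0.084%. Met.

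If the failed exchange is instead one of 44 started, Cohort 2 gives 1/44 = 0.117%, still not met. Cohort 1 then has 105 − 43 = 62 eyes and 1 − 0.95^(1/62) = 0.083%, still met. The crossover lies between 51 eyes (0.1005%) and 52 eyes (0.0986%). A single event therefore reverses the result only while Cohort 2 has at most 51 eyes and Cohort 1 at least 52.

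**3. SSI, threshold 0.8%**

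Assume each failed exchange would count as one SSI unless excluded, with no other SSI:

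| Placement | Two failures | Three failures |
|---|---|---|
| Cohort 1, no exclusion visible | 2/61: 0.586%, met | 3/61: 1.354%, not met |
| Cohort 2, exclusion applied | 0, met | 0, met |
| Cohort 2, exclusion not applied | 2/46: 0.778%, met | 3/47: 1.762%, not met |

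**4. Exchange feasibility**

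In a cohort finalized on success, completion is 100% by construction. Among 44 started exchanges, two failures would give 42/44 = 95.5% (one-sided exact 95% lower limit 86.4%). Five would give 39/44 = 88.6% (77.6%).

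**5. Follow-up**

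The 3 Month Visit falls on Day 80 to 100 and the exchange 1 to 21 days later, so on Day 81 to 121. On the Cohort 1 schedule the last visit (Day 330 to 420 from surgery) comes 330 − 121 = 209 to 420 − 81 = 339 days after the attempt. On the Cohort 2 schedule it comes 330 to 420 days after. Section 3.1 promises 12 months from the later of surgery and exchange, but gives no visit list for this case.

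**The case against.** **The documents can be read together.** A reader might infer that they hold three competing entry rules: election, procedure and success. They do not support that. Section 3.3.4 records a prospective cohort first and finalizes it later, which accounts for the election wording in the synopsis and 3.1. The synopsis also lists the cohorts, for analysis, simply as eyes with and without exchange, which agrees with the SAP. What survives is the difference between success in 3.3.4 and 3.3.6 and procedure in the SAP.

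**The adverse events are not lost.** A reader might infer that events from failed exchanges vanish. Section 3.3.6 requires them to be recorded at the exchange visit. Protocol 8.3.1.1 pools ISO events over both cohorts to 12 months. SAP 5.5 plans AE summary tables with intra-operative events shown separately. The SAP's All HMIOL Eyes Cohort is "restricted to 1 Day, 1 Week, 1 Month, and 3 Months following primary cataract extraction (PCE" and so stops before the exchange, but it is not the only overall summary.

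**No eye need fall outside both cohorts.** One might set the Cohort 2 result with the failed eye against 0/44 with it left out altogether. SAP Cohorts 1 and 2 are complementary, so complete omission is unlikely. The fair comparison is Cohort 2 against Cohort 1, as above.

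**The illustration is fragile.** It uses assumed failures and termination minimums, and with about 45 eyes any single event exceeds 0.1%. That is correct: it shows that classification can decide the result, not that it will. The SAP also says its tests are not meant for definitive regulatory conclusions, though they are meant to support a confirmatory study.

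**Some sources are unseen.** Several endpoints are redacted, the SAP's Safety Population text is not shown, and the Surgical Guide and Manual of Procedures are separate. Reporting of attempted exchanges therefore cannot be called absent.

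**Conclusion.** The point holds as an inconsistency that should be fixed. The protocol makes Cohort 2 membership depend on success; the SAP does not, and does not say whether a started procedure counts. For an exchange started but not completed, with the HMIOL retained, the cohort, the scheduled visits, the SSI exclusion and entry to the ECC test all depend on which text is applied.

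The error lies in the cohort-level rates and the exchange-feasibility result, not in total loss of adverse events. If the SAP wording is read to include started exchanges, the selection on success does not arise; nothing tells the analyst to read it so. In the illustration, one event moves from 0.114% (not met) to 0.084% (met) against a 0.1% threshold. That rests on at least one failed exchange, an event in that eye, and cohorts near the termination minimums. With no failed exchanges the point has no numerical effect.

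**What to change.** (a) In both documents, define Cohort 2 for safety and feasibility as every eye in which an optic exchange was started, with completed exchanges as the effectiveness subset. Let only exchanges never started revert to Cohort 1. State how the SSI exclusion (Protocol 7.1, SAP 5.4) and the ECC test treat failed attempts.

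(b) Report completed over attempted exchanges with an exact confidence interval.

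(c) Reconcile Protocol 3.1, 3.3.5, 3.3.7 and 4.5 on which scheduled visits apply after an exchange that was started but not completed. The choice of schedule is for the sponsor and investigators.

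Cost: wording in the synopsis, Protocol 3.1, 3.3.4 to 3.3.7, 4.5 and 7.1, and SAP Sections 4 and 5.4, plus one table. An attempt-outcome field may be needed in the eCRF, since the details listed in 3.3.6 include surgery date and times but no outcome. The downside is slightly less favourable Cohort 2 rates. The definition should be settled before outcomes of failed attempts are known.

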3.3.5 COHORT 1: 6 AND 12 MONTH VISITS

All subjects entered into Cohort 1 will be seen for 6 and 12 Month Visits (post-primary cataract extraction) for bilateral assessments and exited from the study (See Appendix A – Table 1).

NOTE: All concomitant medication, AE, ADE, DD, and SAE collection must be continued throughout the course of the study.

3.3.6 COHORT 2: OPTIC EXCHANGE VISIT (3 MONTH VISIT +1-21 DAYS)

Record any changes in concomitant medications and prepare the subject for optic exchange surgery in the study eye (see Surgical Procedure Guide).

CLARVISTA MEDICAL

PROTOCOL CP-00001 Rev.05

The Investigator will carry out the optic power determination, surgical procedure, and HMIOL optic exchange as specified in the Surgical Guide and the following details will be captured in both Source Documents and eCRFs:

- Date of surgery
- Operative eye
- Incision location and size
- Ophthalmic Viscoelastic Device (OVD) used
- All medication used pre-, intra-, and post-operatively (ophthalmic and systemic)
- Surgical times
- Model, serial number, and diopter of HMIOL Optic
- HMIOL Optic injection device

Once the subject is confirmed stable post-surgery, provide IRB / EC approved post-operative instructions and discharge.

Following successful completion of HMIOL optic exchange, the subject is entered into Cohort 2. Record any AEs, ADEs, UADEs, or DDs (see Sections 6.1.1, 6.1.2, 6.1.3, or 6.1.4 respectively) observed pre-, intra-, or post-operatively.

3.3.7 COHORT 2: POST-OPERATIVE VISITS (DAYS 1 - 420 POST-OPTIC EXCHANGE VISIT)

All subjects in Cohort 2 will be seen for 1 Day, 1 Week, 1 Month, 3 Month, 6 Month and 12 Month (post-optic exchange) assessments. (see Appendix A – Table 3).

NOTE: All concomitant medication, AE, ADE, UADE, DD, and SAE collection must be continued throughout the course of the study.

3.3.8 UNSCHEDULED VISITS

If at any time during the study, outside of the above scheduled visits, the subject requests or the Investigator determines the subject should be assessed, an unscheduled visit may occur. Adverse events and concomitant medications will be recorded and assessments deemed necessary by the Investigator should be performed on either or both eyes. NOTE: Only data relevant to the primary study eye (if applicable) will be captured on the Unscheduled Visit eCRFs.

If a subject is seen for multiple visits during a given visit window, the data from a visit that is intended to meet the protocol requirements for the scheduled visit should be captured in the visit eCRF. Where such a determination cannot be made, the first visit within the scheduled visit window will be used for completion of the protocol required visit. If assessments are missing from that visit, however captured at subsequent visits within window, those assessments can be collected as part of the protocol visit. In such a circumstance, the visit date will remain consistent with the first visit established within the visit window, per the scenario above. Any additional and applicable data captured and associated with the Study Eye will be captured as an Unscheduled Visit.

3.3.9 MISSED VISITS

CLARVISTA MEDICAL

PROTOCOL CP-00001 Rev.05

If a subject misses any scheduled visit and cannot be seen prior to the start of the next visit window, the visit will be considered "missed."

4.0 STUDY METHODS

Prior to recruitment of any subjects into the study, review and written approval of the protocol and informed consent must be obtained from the Institutional Review Board (IRB) or Ethics Committee (EC) by each participating clinical site.

4.1 INFORMED CONSENT

Informed consent must be obtained and documented in writing prior to the initiation of any study procedures. The subject (or the subject's legally authorized representative) must be allowed sufficient time to thoroughly read (or have explained), the informed consent form. The Investigator or his/her designee should answer any questions that the subject/representative might have. If the subject agrees to participate in the study, (i.e. provides informed consent) the subject/representative must sign two copies of the informed consent form. The witness and the Investigator must also sign both copies of the informed consent form. One copy of the informed consent form should be given to the subject/representative. If applicable, it will be provided in a certified translation of the local language. As part of the consenting process, the subjects will be informed of their right to treatment for any injuries related to the study. Any and all such treatment if necessary, will be paid for by the Sponsor to the extent it is not covered by a subject's healthcare coverage (subject to local ethics committee approval). Completion of the consenting process as well as the date of the subject's signature on the informed consent form should be noted in the subject's medical chart.

Subjects who complete the informed consent process will be screened for eligibility. Screened subjects will be recorded on site-specific screening logs and once they are determined as being eligible, they will be enrolled into the study and an HMIOL order placed with the Sponsor if necessary. All eligible subjects will receive a stipend to attend scheduled study visits as an allowance for food, time, and travel expenses.

Subjects will complete the Investigator's standard of care (SOC) consent process for the FE procedure.

Subjects scheduled for an optic exchange will complete an addition IRB / EC approved informed consent process for this procedure.

4.2 ASSIGNMENT OF SUBJECT IDENTIFICATION

A unique and sequential subject identification number (ID) will be assigned at screening and never duplicated for another subject. This ID will be used on all study-related documents. To maintain confidentiality, the subject's name will not be recorded on any study document other than the informed consent form.

4.3 SCREEN FAILURE

A record of screen failures and the reasons for the screen failures will be recorded in the subject source documents and captured in the eCRF for summary.

4.4 SUBJECT COMPLETION

CLARVISTA MEDICAL

PROTOCOL CP-00001 Rev.05

The subject has completed the entire study when the HMIOL has been implanted and / or the Optic Exchange completed and the Sponsor receives completed electronic Case Report Form (eCRF) documentation for all visits and a Study Exit eCRF. Subjects who require further follow-up for an AE will be followed according to Section 6.3.4.

A Study Exit eCRF must be completed for all subjects who complete the clinical investigation.

4.5 SUBJECT DISCONTINUATION

A subject **MUST** be discontinued prior to the final study visit for any of the following reasons:

- Death
- Subject is enrolled and scheduled for surgery but is not implanted with an HMIOL at Day 0 (Operative Visit – Primary Cataract Extraction)
- Surgical complication(s) unrelated to the investigational device preventing the implantation of the HMIOL (i.e. capsulorhexis tear, zonular rupture, evident zonular weakness or dehiscence, posterior capsular rupture, vitreous loss, posterior capsular plaque, significant detached Descemet's membrane, significant anterior chamber bleeding, iris incarceration or damage, corneal endothelial touch, unsuccessful/incomplete phacoemulsification, haptic and/or optic damage/haptic amputation)
- Explantation of the HMIOL System

If the study lens is explanted, one postoperative visit should be completed to record best-corrected distance visual acuity (BCDVA) before the subject is discontinued.

Subjects who withdraw from the study will be asked to complete procedures outlined in the 12 Month Visit (if withdrawn prior to that visit). Subjects who are terminated due to an AE will be followed, if possible, at least until resolution or stabilization of the AE. Subject withdrawals will be documented clearly on the source document and applicable eCRF.

Prior to discontinuing a subject, every effort should be made to contact the subject, schedule a final study visit, and obtain as much follow-up data as possible. Adverse events will be followed as described in Section 6.3.4. Discontinued subjects should be followed outside of the study protocol according to the Investigator's normal postoperative standard of care.

A Study Exit eCRF must be completed for all subjects who discontinue from the clinical investigation.

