8.3 STATISTICAL METHODS

The data analyses will be based on the analysis populations described above. No imputation for missing data will be performed. The statistical summaries will be prepared for HMIOL Cohort 1, HMIOL Cohort 2, and HMIOL eye Cohort (Cohort 1 + Cohort 2). For some selected outcomes, the summaries will be prepared for the fellow eye cohort.

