8.3.2.1 BCDVA

The LogMAR will be derived for BCDVA. The descriptive statistics for continuous variables will be used to summarize LogMAR BCDVA at each visit based on the implanted-eye population for the three different lens cohorts (HMIOL Cohort 1, HMIOL Cohort 2, and Fellow-eye Cohort). The data at preoperative and 3-month post-primary-surgery will also be summarized for the HMIOL-eye cohort.

Additionally, the number and percentage of eyes reaching BCDVA 20/40 or better at each visit will be prepared for Cohort 1, Cohort 2, and the Fellow-eye Cohort. The one-sided upper 95% confidence limit of the proportion of HMIOL eyes with 20/40 or better will be calculated based on the binomial distribution and compared to a target of 0.925. If the confidence limit is > 0.925 , then the null hypothesis of $p \geq 0.925$ will not be rejected.

The analyses will be repeated based on the Per Protocol Population and the Best-case Population.

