5.1. General Statistical Methods

For continuous measures, descriptive summary statistics will include the number of observations, mean, standard deviation, median, minimum, maximum, as well as the number of eyes with results not reported. For continuous measures analyzed as changes from earlier visits, the 95% confidence interval for change will also be reported. Continuous measures may also be dichotomized or otherwise split into clinically meaningful categories and additionally analyzed as categorical measures.

For categorical measures, the percentage and number of cases for each condition (e.g., 20/20 or better) will be reported. The number of eyes without results will be omitted from the numerator and denominator of such calculations (i.e., no imputation will be performed).

Any calculated p-values will be based on nominal calculations with no adjustment for multiplicity.

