5.3. Accountability

Accountability will be based on eyes (not subjects). The number and percentage of eyes available for analysis at each time point will be presented. For eyes not available for analysis, a breakdown will be provided to summarize the following reasons for missing data: subject discontinued, missed study visit but seen later, missed study visit but subject accounted for (i.e., contacted), and lost-to-follow-up. Eyes for active subjects at a time point, defined as those enrolled but who have not yet reached the corresponding time point, will also be summarized. Accountability as a percentage will be calculated based on the total number available for analysis over the total number of subject eyes enrolled minus total number discontinued and the total number active.

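### Eyes whose HMIOL is explanted generally drop out of the later BCDVA and MRSE success rates and out of the accountability denominator, which tends to flatter both

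*Protocol*

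**What the plan says.** Protocol 4.5 lists "Explantation of the HMIOL System" among the reasons for which a subject must be discontinued before the final visit. The follow-up tied to it is short: "If the study lens is explanted, one postoperative visit should be completed to record best-corrected distance visual acuity (BCDVA) before the subject is discontinued". No refraction is required at that visit and no timing is given for it.

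Protocol 8.3 states: "No imputation for missing data will be performed". SAP 5.1 applies the same principle to categorical measures: "The number of eyes without results will be omitted from the numerator and denominator of such calculations". SAP 5.3 defines accountability as the "total number available for analysis over the total number of subject eyes enrolled minus total number discontinued and the total number active". SAP 8 plans no sensitivity analyses.

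The rates concerned are listed by study visit in Protocol 7.2 and SAP 5.6: BCDVA 20/40 or better, and MRSE within 0.50 D and within 1.00 D of target. For BCDVA there is also a formal comparison in Protocol 8.3.2.1: "The one-sided upper 95% confidence limit of the proportion of HMIOL eyes with 20/40 or better will be calculated" and compared with 0.925. The null hypothesis, p >= 0.925, stands when that limit exceeds 0.925. SAP 4 follows the All HMIOL Eyes Cohort only to 3 months, so under the SAP the later rates belong to Cohorts 1 and 2.

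**The concern.** Most missing data in a lens trial can be argued to be unrelated to the result. Explantation cannot: it means the lens did not stay in the eye, and the protocol itself then ends follow-up. The available-data rule leaves such an eye out of every later rate for which it has no result, and no rule in the visible text says how it should count.

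If the omitted eyes would mostly not have met the endpoint, two things happen. The observed proportion rises, and the sample shrinks, which widens the interval. Both push the upper limit up, and a higher limit is the favourable outcome when the null hypothesis is p >= 0.925. The SAP says these results are meant to support a confirmatory study, so an inflated 12-month rate could carry into its planning.

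**Working it through.** **Inputs.** Target 0.925, one-sided 0.05, true p = 0.85, N = 100 and stated power 0.753 (Protocol 8.1). A minimum of 44 optic exchanges (Protocol 4.7.1), used here as a possible size for Cohort 2. The documents give no explant rate, so the explant counts below (1, 3 or 5 per 100; 1 per 44) are assumptions. No other data are assumed missing.

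**Step 1: reproduce the plan's figure.** Exact binomial: take the largest c with P(X <= c | n, 0.925) <= 0.05; power is P(X <= c | n, 0.85). At n = 100, c = 87 (exact alpha 0.0364) and power is 0.7527, matching 0.753. The other rows of the table also agree to three decimals.

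**Step 2: upper limits with and without the explanted eyes.** The limit is Clopper-Pearson, one-sided 95%: the 0.95 quantile of Beta(x + 1, n - x). In the last column the explanted eyes count as not achieving the endpoint.

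| Assumed case | Explanted eyes omitted | Explanted eyes in denominator |
|---|---|---|
| 100 eyes, 1 explant | 87/99 = 87.9%, limit 0.9285, not rejected | 87/100 = 87.0%, limit 0.9214, rejected |
| 100 eyes, 3 explants | 85/97 = 87.6%, limit 0.9270, not rejected | 85/100 = 85.0%, limit 0.9052, rejected |
| 100 eyes, 5 explants | 83/95 = 87.4%, limit 0.9255, not rejected | 83/100 = 83.0%, limit 0.8887, rejected |
| 44 eyes (Cohort 2), 1 explant | 37/43 = 86.0%, limit 0.9374, not rejected | 37/44 = 84.1%, limit 0.9229, rejected |
| 100 eyes, 5 explants, away from border | 88/95 = 92.6%, limit 0.9649, not rejected | 88/100 = 88.0%, limit 0.9293, not rejected |

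The first four rows are the lowest success counts that still pass when explants are omitted, chosen to show the border.

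**Step 3: how wide the border is.** With 3 explants in 100, the rejection cut-offs are 84 (n = 97) and 87 (n = 100), so the result differs only for 85, 86 or 87 successes. The binomial chance of landing there among 97 retained eyes is about 22% if their success rate is 0.85, 34% at 0.90, 16% at 0.925, 2% at 0.95 and below 0.1% at 0.97.

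**Step 4: effect on detecting a low rate.** Suppose the all-eyes rate is 0.85 with explants as non-achievers, N = 100. With k explants, the retained-eye rate is 85/(100 - k). The chance of rejecting p >= 0.925 when explants are omitted is 0.66, 0.42 and 0.20 for k = 1, 3 and 5. With them kept in the denominator it is 0.76, 0.77 and 0.79.

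**Step 5: effect on the rate itself.** This needs no hypothesis test and applies equally to MRSE. A 90% rate in retained eyes is 0.90 x (100 - k)/100 of all eyes: 89.1%, 87.3% and 85.5% for k = 1, 3 and 5.

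**Step 6: accountability.** With 100 eyes, 5 explants and no other loss, the SAP 5.3 formula gives 95/(100 - 5) = 100%, against 95/100 = 95% of enrolled eyes. With 5 more eyes missing, it gives 90/95 = 94.7%, against 90%.

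**The case against.** Several counter-arguments have force.

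- **The exclusion is inferred.** No sentence excludes explanted eyes. They stay in the Implanted-Eye Population, and SAP 5.1 drops only eyes without results. Protocol 3.3.8 lets data from a visit inside a scheduled window serve as that visit, and Protocol 4.5 also asks for as much follow-up as possible. This stands, which is why the point says the eyes are generally, not always, left out. One explant visit can serve at most the window it falls in, and it need not yield an MRSE.
- **Part of the SAP is not visible.** Section 6, the start of Section 7 and some redacted text cannot be read, so a handling rule there cannot be ruled out.
- **The pooled example does not match the SAP at 12 months.** This stands. Under SAP 4 a pooled analysis is affected only up to 3 months, and the later effect falls on the smaller Cohorts 1 and 2. The 44-eye row is the closer illustration there.
- **Explants are recorded elsewhere.** They are reported to the sponsor within 24 hours (Protocol 6.3.1), appear as discontinued in the SAP 5.3 breakdown, and probably count as secondary surgical interventions, though no passage says so outright. If they do, 3/100 has an exact lower 95% bound of 0.0082, above the 0.8% threshold in SAP Table 1. A reader might infer that the plan hides explants; it does not. But these displays do not correct the effectiveness rates or the accountability percentage.
- **An explanted eye may still see 20/40.** BCDVA is best-corrected and is measured after explant. Scoring the eye as a failure in the main BCDVA result would turn an acuity rate into a composite of acuity and lens retention. This stands, and it argues against replacing the available-data result.
- **Feasibility status.** SAP 4 says the tests are not for definitive conclusions. That limits the stakes, but the rates are still meant to inform a confirmatory study.

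**Conclusion.** The point holds in a bounded form. Mandatory discontinuation after explant, combined with omission of eyes without results, generally leaves explanted eyes out of the BCDVA and MRSE proportions at later visits. The rates tend to be biased upward and the BCDVA comparison towards not rejecting p >= 0.925, provided the omitted eyes would achieve the endpoint less often than the retained ones. The accountability percentage rises as well, because it subtracts the same eyes.

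The size depends on an explant count that the documents do not give. At an assumed 1 to 5 explants per 100, a 90% rate in retained eyes corresponds to 89.1% down to 85.5% of all eyes.

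A reader might infer that a few explants would by themselves reverse the BCDVA conclusion. The calculations do not support that in general: reversal needs a result near the border and explanted eyes that do not count as successes. Nor do the documents support the reading that only eyes still holding the lens can ever enter a later rate, since an in-window explant visit could contribute BCDVA.

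**What to change.** In SAP 5.1 and 5.6, prespecify a second set of proportions beside the available-data rates: BCDVA 20/40 or better, MRSE within 0.50 D and MRSE within 1.00 D, with explanted eyes kept in the denominator and counted as not achieving the endpoint with the HMIOL at all visits after explant. Report the BCDVA recorded at the post-explant visit alongside, so that good acuity after explant is visible.

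In SAP 5.3, give explants their own line, separate from other discontinuations, and add an accountability percentage that does not subtract them.

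The available-data rates and the protocol's discontinuation rule are left as they are. The cost is SAP wording and one more set of tables, with no new visits or data. The added rates will be slightly less favourable.
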